## PREFACE

The purpose of this document is to provide a Manual of Operating Procedures (MOP) for the SMART Supplement Project 5a — Intrapersonal Stigma Reduction. The role of the MOP is to facilitate consistency in protocol implementation and data collection across participants and study staff. Use of the MOP increases the likelihood that the results of the study will be scientifically credible and provides reassurance that participant safety and scientific integrity are closely monitored.

## OVERVIEW

### Objectives

The goal of this project is to develop and evaluate the efficacy of a stigma reduction intervention that functions at the Intrapersonal (individual) level. Our intervention will address this cost/benefit evaluation among individuals known to face intersecting stigma of alcohol or substance use disorder and African American race, with treatment elements chosen explicitly to increase the value of treatment using salient forms of reward, and to ease perceived costs through explicit services in an effort to encourage the occurrence of the first treatment visit.

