### Design and Outcomes

This project consists of a pre-post survey, separated by a two-week interval. All elements of our individual intervention are based in Behavioral Economics theory, with the intention of increasing benefits and reducing costs to facilitate individual decision making and reduce subsequent experienced, anticipated, and associative stigma for the individual seeking treatment.

The primary outcome for Project A is reduction in stigma at two weeks post intervention. This will be assessed by using the Substance Use Stigma Mechanisms Scale.

Secondary outcomes include Addiction Treatment visit attendance (e.g., did they attend the visit that was scheduled?) and Feedback and Satisfaction with treatment.

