## **Duration**

Participants will be enrolled at baseline (week 0) and will have one follow-up assessment to be completed two weeks after enrollment.

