## **Sample Size and Population**

Approximately 50 participants will be recruited from the Frayser community of Memphis, at the recruitment site of Legacy of Legends (or associated venue, as dictated by Legacy events). Participants must identify as having a substance use problem and must not currently be in treatment. All participants must be over age 18, able to understand consent procedures, reside in the Frayser community, identify as African American or mixed race, and have access to a telephone for retention/follow up.

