## PROCEDURES

### Cascade of Events

#### Baseline

- Engage with potential participants to provide information about participation.
- If interested, complete screening for eligibility/exclusionary criteria.
- Complete informed consent.
- After participants have signed the informed consent form, we will collect the remaining baseline data and deliver the intervention.
  - Administer assessments which include contact information, demographics, and SU-SMS (stigma scale)
  - Deliver intervention
  - Offer to help schedule appointment at CAS (or other clinic)

- Set appointment date/time for 2-week follow-up visit or call.
- Provide a \$20 Kroger gift card as compensation for enrollment.
  - Kroger gift cards will be given via a hard copy gift card following the [incentive procedures](#).
- If the participant schedules a visit and needs transportation support, schedule a Lyft ride
- Provide participant your contact information to ensure that the Lyft ride can be changed as needed (Lyft is scheduled only through us, not the participant).

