## SU-SMS

How often have people treated you this way in the past because of your alcohol and/or drug use history?  
Please circle your response.

		Never	Not often	Somewhat often	Often	Very Often
1.	Family members have thought that I cannot be trusted.	1	2	3	4	5
2.	Family members have looked down on me.	1	2	3	4	5
3.	Family members have treated me differently.	1	2	3	4	5
4.	Healthcare workers have not listened to my concerns.	1	2	3	4	5
5.	Healthcare workers have thought that I'm pill shopping, or trying to con them into giving me prescription medications to get high or sell.	1	2	3	4	5
6.	Healthcare workers have given me poor care.	1	2	3	4	5

How likely is it that people will treat you in the following ways in the future because of your alcohol and/or drug use history?

		Very unlikely	Unlikely	Neither unlikely nor likely	Likely	Very likely

1.	Family members will think that I cannot be trusted.	1	2	3	4	5
2.	Family members will look down on me.	1	2	3	4	5
3.	Family members will treat me differently.	1	2	3	4	5
4.	Healthcare workers will not listen to my concerns.	1	2	3	4	5
5.	Healthcare workers will think that I'm pill shopping, or trying to con them into giving me prescription medications to get high or sell.	1	2	3	4	5
6.	Healthcare workers will give me poor care.	1	2	3	4	5

How do you feel about your alcohol and/or drug use history?

		Strongly disagree	Disagree	Neither disagree nor agree	Agree	Strongly agree
1.	Having used alcohol and/or drugs makes me feel like I'm a bad person.	1	2	3	4	5
2.	I feel I'm not as good as others because I used alcohol and/or drugs.	1	2	3	4	5
3.	I feel ashamed of having used alcohol and/or drugs.	1	2	3	4	5

4.	I think less of myself because I used alcohol and/or drugs.	1	2	3	4	5
5.	Having used alcohol and/or drugs makes me feel unclean.	1	2	3	4	5
6.	Having used alcohol and/or drugs is disgusting to me.	1	2	3	4	5

TREATMENT INITIATION		
Did you go to any facility for substance use treatment since we last spoke?	Yes	No
If yes, where did you get treatment?		

FEEDBACK & TREATMENT SATISFACTION				
1.	How interesting did you find this study?	Totally bad, boring	OK	Excellent, it was great
2.	What made you want to enroll in this study? (select all that apply)	I wanted help getting treatment	Gift cards	Other _____
3.	How personally relevant did you find this study?	Not at all relevant	Somewhat relevant	Very relevant

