Reducing Stigma towards Opioid Use Disorder on Interpersonal and Intrapersonal Levels

Statistical Analysis Plan

NCT04693416

12/7/2022

Preliminary data analyses will include studies of patterns of missing data, dropout rates, distributional properties of measures, and correlations among assessment measures. Continuous variables showing significant skewness or kurtosis will be analyzed with methods not sensitive to these features or will be transformed using standard approaches (such as Box-Cox transformations). Because all analyses will focus on feasibility and satisfaction and determining preliminary intervention effect sizes (with less concern focused on testing for statistical significance), outcome analyses will be conducted using a separate analysis for each outcome at the follow up observation.

Individual (intrapersonal) changes in stigma pre/post intervention will be conducted using paired sample t-test/Wilcoxon signed-rank test. Individual treatment uptake (agreement to set up an appointment and attendance at the appointment) will be included as secondary correlational analyses to evaluate relations with stigma scores. Comparisons with archival data will be conducted using a Chi Square analysis/Fisher's exact test. Family/Support (interpersonal) pre/post intervention outcomes will be conducted using paired sample t-test/Wilcoxon signed-rank test. Community assessment baseline and follow up data will be entered into a 2 (baseline vs. follow up) by 2 (intervention vs. comparison) analysis of variance (ANOVA) which will yield effect sizes for time, and interactions of time by intervention group. The primary dependent variable will be stigma score. We hypothesize that stigma scores will be lower in the intervention community.

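### The intrapersonal study is set up to evaluate efficacy, but as a single-group pre-post study with no comparator for the stigma score it can only estimate change

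*Protocol*

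**What the plan says.** The Protocol's Objectives section sets the goal as to "develop and evaluate the efficacy of a stigma reduction intervention" at the individual level. The next section, Design and Outcomes, describes the design: "This project consists of a pre-post survey, separated by a two-week interval". It names the primary outcome: "The primary outcome for Project A is reduction in stigma at two weeks post intervention", measured with the SU-SMS.

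Under Sample Size and Population, "Approximately 50 participants will be recruited from the Frayser community of Memphis". Under Procedures, Baseline, once consent is signed, "we will collect the remaining baseline data and deliver the intervention", with no allocation step. Under Duration, each participant "will have one follow-up assessment to be completed two weeks after enrollment".

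The SAP says its analyses focus on feasibility, satisfaction and "determining preliminary intervention effect sizes (with less concern focused on testing for statistical significance"). For the intrapersonal component it names a paired t-test or Wilcoxon signed-rank test of the pre/post difference and nothing between groups.

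**The concern.** Efficacy is a causal claim: stigma is lower than it would have been without the intervention. A single-group pre-post study does not observe what would have happened without it. The SAP's wording is more modest, but it still attaches the word intervention to an effect size that, for this component, is only a change over time.

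At stake is what the study may conclude. A fall in the SU-SMS score could be read as evidence that the intervention works when the data show only that scores fell. The Protocol and the SAP also state different aims for the same data, and a reader cannot tell which governs.

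**Working it through.** **1. Is there a comparator for the individual stigma score?** Three places in the SAP could supply one.

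- *Intrapersonal pre/post analysis.* A paired test within one group. No comparator.
- *Archival comparison.* The named tests are Chi-square and Fisher's exact, and the sentence follows the one on treatment uptake. It fits a categorical outcome such as attendance. Its outcome and source are not stated, but it is not a comparison of SU-SMS scores as the plan treats them elsewhere.
- *Two-by-two ANOVA, intervention versus comparison.* This belongs to the community component.

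The Protocol describes no control, wait-list or randomisation. So there is none.

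**2. What does the paired analysis estimate?**

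Expected change = intervention effect + non-specific shift.

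The paired test asks whether this sum is zero. One group measured twice gives one equation for two unknowns.

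**3. Is a non-specific shift plausible from the documents?**

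- *Retest:* the same items are asked at both visits.
- *Demand:* staff read the items aloud and record the answers (Data Collection), and the Research Coordinator is trained in both data collection and intervention delivery (Pre-Initiation Training). At follow-up, unlike at baseline, the respondent has been through the session.
- *Time and mode:* a missed follow-up may be made up over two further weeks, by phone or in person (Retention).

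The documents do not say how large the sum of these would be, or in which direction.

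**4. Illustration of size.** The plan has no figure to reproduce: neither document gives an alpha, power, effect size, SD or dropout rate. The sample of about 50 is from the Protocol. The rest is assumed: two-sided alpha 0.05, no true intervention effect, a favourable shift d in SDs of the change score, and 50 or 40 completers.

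P(significant) = P(|T| > t), where T is noncentral t with n − 1 degrees of freedom and noncentrality d√n. For n = 50, t = 2.010; for n = 40, t = 2.023. Example: d = 0.2 and n = 50 give noncentrality 0.2 × 7.071 = 1.414 and probability 0.284.

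| Assumed shift d | n = 50 | n = 40 |
|---|---|---|
| 0.05 | 6% | 6% |
| 0.1 | 11% | 9% |
| 0.2 | 28% | 23% |
| 0.3 | 55% | 46% |

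**5. Would splitting the sample solve it?** With 25 per group, 80% power and two-sided 0.05 (both assumed), the detectable difference in change is (1.960 + 0.842) × √(2/25) = 0.79 SD by the normal approximation, or 0.81 SD using the t distribution. A control group at this sample size would detect only a large difference.

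**The case against.** The strongest reply is that this is a small pilot under a one-year supplement. The SAP says openly that it aims at feasibility and preliminary estimates and plays down significance testing, and the Protocol calls the design a pre-post survey in the section right after the objective. On that view only one overview sentence is too strong.

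Much of this stands. The design is a defensible pilot choice, step 5 shows why a control group need not be demanded, and the SAP's framing limits how serious the point is. But less emphasis on p-values does not turn an uncontrolled change into an intervention effect, and the SAP keeps that label.

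Three stronger readings are tempting, and the documents do not support them.

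- *That a significant result will be reported as efficacy or used to size a later trial.* Neither document states a success rule or a later trial.
- *That the test has an inflated error rate.* It keeps its level for its own null of zero mean change. The table's percentages also depend on an assumed drift in the favourable direction; an unfavourable drift of 0.2 SD would give a favourable significant result in under 0.1% of trials.
- *That the six past-treatment items can serve as a negative control.* Their stem reads "How often have people treated you this way in the past because of your alcohol and/or drug use history", which suggests they should hardly move in two weeks. But Design and Outcomes names experienced stigma among the things the intervention is meant to reduce, and a session on the stigma of addiction could change how past treatment is recalled. Movement on these items would be ambiguous.

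The gift card is also a weak candidate: the same $20 is given at both visits, so it would bias the change only if its effect differed between them.

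**Conclusion.** The point holds as a mismatch between the stated aim and the design. The Objectives claim a property the intrapersonal study lacks, and the SAP's effect-size label does not repair it. This rests on the documents alone and needs no numerical assumption.

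The size of any misattribution is unknown. On the assumed inputs, the chance of a significant change with no true effect runs from about 6% (shift of 0.05 SD) to 55% (0.3 SD) at 50 completers, and from 6% to 46% at 40. This is an illustration of what the change score can absorb, not an estimate for this trial.

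**What to change.** 1. In the Protocol's Objectives, replace the efficacy wording with: *estimate the pre-post change in stigma after* the intervention. This brings the aim into line with the SAP's preliminary purpose.
2. In the SAP, describe the intrapersonal stigma result as within-person change with a confidence interval, and say it is not attributable to the intervention alone.
3. If changes on the SU-SMS subscales are shown, report them descriptively only, with no role as a control.

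This needs two edits and no new data, participants or visits. The downside is that the stated claim becomes less favourable to the intervention.

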### Design and Outcomes

This project consists of a pre-post survey, separated by a two-week interval. All elements of our individual intervention are based in Behavioral Economics theory, with the intention of increasing benefits and reducing costs to facilitate individual decision making and reduce subsequent experienced, anticipated, and associative stigma for the individual seeking treatment.

The primary outcome for Project A is reduction in stigma at two weeks post intervention. This will be assessed by using the Substance Use Stigma Mechanisms Scale.

Secondary outcomes include Addiction Treatment visit attendance (e.g., did they attend the visit that was scheduled?) and Feedback and Satisfaction with treatment.

## **Duration**

Participants will be enrolled at baseline (week 0) and will have one follow-up assessment to be completed two weeks after enrollment.

## **Sample Size and Population**

Approximately 50 participants will be recruited from the Frayser community of Memphis, at the recruitment site of Legacy of Legends (or associated venue, as dictated by Legacy events). Participants must identify as having a substance use problem and must not currently be in treatment. All participants must be over age 18, able to understand consent procedures, reside in the Frayser community, identify as African American or mixed race, and have access to a telephone for retention/follow up.

## **IRB**

**Project number:** 20-07852-XP

The University of Tennessee Health Science Center IRB (FWA00002301) is the reviewing IRB for this study. Initial approval was received on **02/05/2020**.

## **Award Information**

**Funding Agency:** National Center for Complementary & Integrative Health (NCCIH)

**Award number:** 3R61AT010604-01S1

**Grant Title:** Behavioral Economics based stigma reduction intervention for low income, African American individuals with Opioid Use Disorder. (3R61AT010604-01S1).

**Grant Years:**

10/1/2020 - 9/30/2021

**Supplement Grant Amount:** \$201,631

## TRAINING PLAN

### Pre-Initiation Training

The Research Coordinator will be trained in data collection, data entry, adverse event collection, incentive distribution, and informed consent procedures by the Project Manager ([name]). [name] will train the coordinator on intervention delivery and fidelity.

### Ongoing Training

Data will be monitored throughout the study so that any quality assurance issues can be handled in a timely manner. Any issues with data collection, data entry, informed consent, and incentive distribution will be monitored by [name] and will be addressed at biweekly staff meetings. Issues regarding study fidelity will be addressed by [name] as needed.

## ELIGIBILITY CRITERIA

Participants must meet the following eligibility criteria to participate in this study:

- Age 18 or older
- Able to understand consent procedures
- Identify as African American or mixed race,
- Access to telephone for retention/follow up
- Self-identified alcohol or substance use disorder (SUD) related issues, and
- Not currently in treatment for SUD.

## PROCEDURES

### Cascade of Events

#### Baseline

- Engage with potential participants to provide information about participation.
- If interested, complete screening for eligibility/exclusionary criteria.
- Complete informed consent.
- After participants have signed the informed consent form, we will collect the remaining baseline data and deliver the intervention.
  - Administer assessments which include contact information, demographics, and SU-SMS (stigma scale)
  - Deliver intervention
  - Offer to help schedule appointment at CAS (or other clinic)

- Set appointment date/time for 2-week follow-up visit or call.
- Provide a \$20 Kroger gift card as compensation for enrollment.
  - Kroger gift cards will be given via a hard copy gift card following the [incentive procedures](#).
- If the participant schedules a visit and needs transportation support, schedule a Lyft ride
- Provide participant your contact information to ensure that the Lyft ride can be changed as needed (Lyft is scheduled only through us, not the participant).

### Follow-Up Visit

- At two weeks post baseline:
- Complete follow-up assessments including SU-SMS, attendance at physician visit, and treatment feedback & satisfaction
- Provide the \$20 Kroger gift card upon completion of visit
  - Kroger gift cards will be given via a hard copy gift card following the [incentive procedures](#).

## Recruitment

Potential participants who are being referred for potential substance use disorder treatment will be recruited by the Research Coordinator I and [name] through Frayser community events, Impact Ministries events, and Legacy of Legends CDC events.

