### Recruitment Script

This is a general script, but can be changed as needed for each situation.

*“Hi, \_\_\_\_! My name is \_\_\_\_ and I am part of the research staff with the Department of Preventive Medicine at the University of Tennessee Health Science Center. You’re here today because you agreed to speak with us about your feelings about drug and alcohol use, and you’re open to hearing about treatment options. We’re doing a research study where we ask people questions, have a discussion, and then ask a few more questions.*

*If you think you might be interested in being in this study, I can ask you a few questions to see if you’re eligible, then we can go through a consent form with you to help you decide if you’d like to participate. Are you interested in seeing if you’re eligible?*

If a person does not wish to participate, we can still provide a handout or information about how to get treatment.

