## MEASURES

### Assessment Schedule

Measure	Baseline	Follow-Up
Contact Information	X	
Demographics	X	
Substance Use Stigma Mechanisms Scale (SU-SMS)	X	X
Agreement to set up intake visit at Center for Addiction Science (or other treatment facility)	X	
Attendance at intake visit at Center for Addiction Science (or other treatment facility)		X

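### The follow-up attendance item counts a visit to any facility, and no baseline measure shown identifies visits arranged before the session

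*Protocol*

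**What the plan says.** **Who is recruited.** Protocol, Recruitment: "Potential participants who are being referred for potential substance use disorder treatment will be recruited", through community events. The Recruitment Script addresses people described as "open to hearing about treatment options". Under Eligibility Criteria, the only rule on treatment status is "Not currently in treatment for SUD".

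**What the intervention is for.** Protocol, Objectives: the intervention is meant "to encourage the occurrence of the first treatment visit".

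**What is recorded before the intervention.** Protocol, Baseline: "Administer assessments which include contact information, demographics, and SU-SMS (stigma scale". The intervention follows, and staff then offer help with booking an intake. The Assessment Schedule adds one baseline uptake measure: "Agreement to set up intake visit at Center for Addiction Science (or other treatment facility".

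**What is recorded afterwards.** The Assessment Schedule lists "Attendance at intake visit at Center for Addiction Science (or other treatment facility". The Treatment Initiation form asks whether the participant has been to any treatment facility since the previous contact and, if so, where.

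**How uptake is defined and used.** Design and Outcomes names attendance as a secondary outcome and explains it as keeping the visit that had been booked. The SAP defines individual uptake as agreeing to an appointment and then attending it, and relates it to stigma scores in secondary correlational analyses. It also states: "Comparisons with archival data will be conducted using a Chi Square analysis/Fisher's exact test". It does not name the variable compared, or the source or population of the archival data.

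**The concern.** The outcome as defined is attendance at a particular appointment. The only attendance item shown records attendance anywhere, whoever arranged it and whenever it was arranged. That gap would matter little in a population with no prior route to care. Here, recruitment draws on people being referred for possible treatment, and a person with a booking already made is eligible. No baseline measure shown would identify that person.

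The intrapersonal project is a pre-post survey with no concurrent control described, so nothing subtracts visits that would have taken place anyway. At stake are the preliminary uptake estimate, its correlation with stigma scores, and any archival comparison that turns out to concern uptake. The direction would favour the intervention if people with a booking attend more often than the rest.

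**Working it through.** **1. The wordings side by side.**

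| Place | Visit that counts | Says who arranged it, or when? |
|---|---|---|
| Protocol, Design and Outcomes | The scheduled visit | No |
| Protocol, Follow-Up Visit | A physician visit | No |
| Protocol, Assessment Schedule | Intake at the named center or another facility | No |
| Protocol, Treatment Initiation form | Any facility since the previous contact | No; asks only where |
| SAP | The appointment agreed to | Implied by the agreement, not stated |

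The form is the broadest of the five, and it is the one that generates the data.

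**2. What the collected data can separate.** Cross baseline agreement with follow-up attendance and location:

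- *Did not agree, attended:* not arranged through the study. It could be an earlier booking or a visit the participant arranged after the session.
- *Agreed, attended a different facility:* probably not the study appointment, with timing still unknown.
- *Agreed, attended the same facility:* could be the study appointment or one booked there beforehand.

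Separation is therefore partial. It flags some visits not arranged through the study but never shows whether a visit was arranged before the session.

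**3. Size.** The documents give about 50 participants and no uptake rate, alpha, power or effect size, so there is no plan figure to reproduce. Every rate below is an assumption.

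Let *f* be the share with a prior booking, *a* their attendance rate and *p* the rate in the others:

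observed rate = *f·a* + (1 − *f*)·*p*, so the rise over *p* is *f*(*a* − *p*).

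With *a* = 0.60 and *p* = 0.20:

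- *f* = 0.10: 0.10 × 0.60 + 0.90 × 0.20 = 0.24, a rise of 4 points.
- *f* = 0.40: 0.40 × 0.60 + 0.60 × 0.20 = 0.36, a rise of 16 points.

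The 4 to 16 points are the rise in the overall rate. The attendance contributed by booked participants is 0.10 × 0.60 = 6 points to 0.40 × 0.60 = 24 points.

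**4. Effect on an archival comparison, if it concerns uptake.** Assume 50 participants, no intervention effect, and a fixed archival rate equal to *p*, so that the archival group has no pre-booked visits. Let *r* be the smallest count whose exact one-sided binomial tail under *p* is at most 0.025.

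| *p* | *f* | *a* | Observed | Extra attenders of 50 | *r* | Tail under *p* | Chance of reaching *r* |
|---|---|---|---|---|---|---|---|
| 0.30 | 0.10 | 0.50 | 0.32 | 1 | 23 | 0.0123 | 0.027 |
| 0.20 | 0.20 | 0.70 | 0.30 | 5 | 17 | 0.0144 | 0.316 |
| 0.10 | 0.40 | 0.70 | 0.34 | 12 | 10 | 0.0245 | 0.990 |

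The first and last rows are the extremes over *p* = 10% to 30%, *f* = 10% to 40% and *a* = 50% to 70%. The SAP's chi-square or Fisher test would treat the archival data as a second sample of a size not given, so these chances are illustrative only. If the archival group had the same *f* and *a*, the rise would cancel.

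**The case against.** **The narrower text governs.** The Protocol puts the booking offer after the intervention, and both Design and Outcomes and the SAP speak of one particular appointment. Read together, they most naturally mean the appointment agreed in the study. This stands. A reader might infer that the plan counts any pre-planned visit as uptake the intervention produced, and the documents do not say so. What remains is that the form does not measure the narrower outcome.

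**Nobody is shown to hold a booking.** The referral is for potential treatment, and the script claims only openness to hearing about options. This stands too: the affected share is unknown and could be small. It cannot be learned from the measures shown.

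**The groups can be separated.** Partly, as the cross-classification shows. A reader might infer that no separation is possible, and that goes too far. The feedback item on how far the study helped the participant start treatment is a rating given afterwards and does not date a booking. The screening form and the intervention script are not in the text available, so what they record cannot be judged.

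**Attendance by a booked person may be a real effect.** The objective is that the visit occurs, and transport support is offered. This is fair, and it is why such people should be reported separately and not removed from the main rate.

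**Uptake is secondary.** The SAP stresses feasibility and effect sizes over significance testing. This limits the weight of the point, but a preliminary estimate still needs to count a defined visit.

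**Conclusion.** The concern holds as a mismatch between outcome and measurement. The follow-up item is broader than the outcome in Design and Outcomes and in the SAP. Given the recruitment source and the single rule on treatment status, a visit arranged before the session can be recorded as attendance and only partly told apart from a study-arranged one.

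The size is not known. Under the assumptions above, overall attendance could rise by 4 to 16 points, or by 1 to 12 attenders of 50 over the wider grid. These figures rest entirely on the assumed booking share and attendance rates, and on the intervention not changing attendance among people already booked.

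A reader might also infer that the archival group is less close to treatment than the participants. The SAP does not describe that group or say that uptake is the variable compared, so this is a possibility to rule out and not a finding. The primary stigma outcome is not affected through this route. The point is worth correcting because the remedy is small.

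**What to change.** 1. Before the intervention, ask whether the participant already has a referral or a booked appointment for substance use treatment.
2. At follow-up, record whether the attended visit was arranged at or after the study session, and through whom.
3. Reconcile the Treatment Initiation form with Design and Outcomes and the SAP by reporting two outcomes: attendance at the study-arranged appointment, and attendance at any facility.
4. Report uptake for all participants, and separately for those with and without a prior appointment. Dropping the booked group from the main rate would change the question and shrink a sample of about 50.
5. State in the SAP that any archival comparison of uptake is not attributable to the intervention unless the archival group was at a similar referral stage. Matching on that stage may not be feasible, since the archival data are not described.

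If enrolment is complete, which the documents do not say, tabulate agreement against attendance and location, and state that the timing of bookings is unknown.

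The cost is one or two extra questions, some SAP wording, and a likely less favourable uptake figure in a smaller subgroup.
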